17.3.2. Safety Analysis

Frequency charts of adverse events occurring at any time during the study will be produced. The proportion of subjects in Arms 1 and 3 reporting one or more adverse events between study entry and Week 24 will be pooled and tabulated. Similar analyses will be done for SAEs and device-related SAEs. Safety analysis will include all subjects who were treated. A Statistical Analysis Plan (SAP) will be developed prior to completion of the first subject in Arm 1 or 3, which may include additional plans for safety analysis.

17.4. Compliance

Compliance will be assessed during the first 24-wks of Arm 1 and Arm 3. Subjects will be instructed to use devices each nights that they report experiencing RLS symptoms. Therefore, percentage compliance with device usage will be calculated using the following formula:

100%*(nights of compliant use)/(total nights with patient-reported RLS symptoms)

Investigational Plan, Protocol CT-05 (Extension Study)

Document #: CT-4

Rev: 1.0

Effective: 11/24/2021

Nights of compliant use will be measured based on digital tracking of the timing and duration of
each NPNS device usage. In cases where digital tracking logs are incomplete or unavailable, the
data will not be included in the compliance analysis.

• A "night of compliant use" will be defined as a minimum of 25 minutes of active NPNS stimulation between noon and noon during an Assessment week.

 "Total assessment nights with RLS symptoms" will be defined as the total nights spent by all subjects in Assessment weeks when the subject reports RLS symptoms on the Weekly questionnaire.

 If a subject is discontinued from the study for reasons unrelated to subject response to treatment, compliance data will only be assessed up until the time of discontinuation. Such reasons could include lack of device availability, personal reasons, or adverse event unrelated to the study device.

17.5. Exploratory Analysis

Additional statistical analysis that is exploratory in nature may be performed with CT-05 data alone and/or with pooled data from CT-05 and from the RESTFUL Study.

18. Remote procedures

During and after the COVID-19 pandemic, replacing some in-person visits with remote interactions may be necessary, for example to reduce risk to subjects and/or to comply with local, state, or federal regulations. In such cases, the study records will indicate which in-person visits were replaced with remote interactions. The allowable study duration may be expanded as needed to allow delay intervals for mailing and receiving programmed devices.

In such cases, one of more of the following approaches may be taken:

1. Remote calibration and training. Remote calibration and training, where possible, will be coordinated by mailing a calibration/training device to the subject, conducting calibration and training via a video call using the calibration/training device, and then mailing programmed

Clinical Trial

Investigational Plan, Protocol CT-05 (Extension Study)

Document #: CT-4

Rev: 1.0

Effective: 11/24/2021

devices to the subject using the settings determined during the calibration. Alternatively, the same devices used in the study may be used for calibration/training.

- 2. Remote follow-up visits. Remote follow-up visits, where possible, will be completed via call or video call, during which the required study assessments will be administered.
- 3. Devices may be returned using a pre-paid mailing label, as needed.
- 4. Remote consent. Remote consent procedures will follow the recommendations set forth in the "FDA Guidance on Conduct of Clinical Trials of Medical Products during COVID-19 Public Health Emergency" [14]. For example, or more of the following procedures listed in the guidance will be used to confirm consent:
 - a. eConsent via a compliant digital platform;
 - b. confirmation of consent by an impartial witness via three-way call or video conference;
 - c. remote explanation of consent followed by in-person signature of informed consent document (to minimize duration of in-person interaction).

19. References

- 1. Allen, R.P. et al. Restless legs syndrome: diagnostic criteria, special considerations, and epidemiology. A report from the restless legs syndrome diagnosis and epidemiology workshop at the National Institutes of Health. Sleep Med. (2003). doi: 10.1016/s1389-9457(03)00010-8

4	Adverse Events (Safety Analysis Population)
5.1	Changes to RLS Management (ITT Population)
5.2	Completion (ITT Population)
5.3	Exposure to treatment, usage (ITT Population)
5.4	Exposure to treatment, stimulation intensity (ITT Population)

Doc #: CL-7 Rev: 2.0 Page 5 of 20

List of Abbreviations

AbbreviationDefinitionAEAdverse Event

CGI-I Clinical Global Impressions – Improvement

FDA Food and Drug Administration FCS Fully Conditional Specification

IRLS International Restless Legs Syndrome Study Group Rating Scale

IRLSS International Restless Legs Syndrome Society

ITT Intent-to-Treat

LOCF Last Observation Carried Forward

MAR Missing at Random

MedDRA Medical dictionary for Regulatory Activities

MOS Medical Outcomes Study

NPNS Non-invasive peripheral nerve stimulation PGI-I Patient Global Impressions – Improvement

PP Per Protocol
PT Preferred Term

RLS Restless Legs Syndrome SAE Serious Adverse Event SOC System Organ Class

SF-36 36-Item Short Form Health Survey

1.0 INTRODUCTION

This document details the analysis plan for the study entitled "Open-label Extension Study to Evaluate Longer-Duration Response to the NTX100 Neuromodulation System for Patients with Medication-Refractory Primary Restless Legs Syndrome (RLS)". It describes the proposed efficacy and safety analyses, including planned summary tables, by-subject data listings, and figures.

A clinical need has been identified of improved treatment for those suffering with primary idiopathic restless legs syndrome (RLS). Patients with RLS have a strong urge with sensations of tingling/pain, usually in their legs, and often present with a primary complaint of not being able to fall asleep regularly. This leads to significant quality of life degradation, depression, daytime sleepiness, lack of productivity, and a host of downstream effects associated with lack of quality sleep.

Restless legs syndrome is a sensorimotor disorder that is characterized by a distressing urge to move the legs and, in some cases, other parts of the body such as arms¹. The diagnosis is made by a response to five hallmark identifying criteria instituted by the International Restless Legs Syndrome Society (IRLSS)², as quoted below:

- "1. An urge to move the legs usually but not always accompanied by or felt to be caused by uncomfortable and unpleasant sensations in the legs.
- 2. The urge to move the legs and any accompanying unpleasant sensations begin or worsen during periods of rest or inactivity such as lying down or sitting.
- 3. The urge to move the legs and any accompanying unpleasant sensations are partially or totally relieved by movement, such as walking or stretching, at least as long as the activity continues.
- 4. The urge to move the legs and any accompanying unpleasant sensations during rest or inactivity only occur or are worse in the evening or night than during the day.
- 5. The occurrence of the above features are not solely accounted for as symptoms primary to another medical or a behavioral condition (e.g., myalgia, venous stasis, leg edema, arthritis, leg cramps, positional discomfort, habitual foot tapping)."

Diagnostically, RLS is considered either primary, often occurring within families, or secondary, developing in association with other conditions (such as iron deficiency anemia, pregnancy, or end-stage renal disease).

In the United States, RLS is believed to affect more than 10 million adults and an estimated 1.5 million children and adolescents³. About one-third of those with RLS symptoms are bothered sufficiently enough to seek medical attention. Epidemiologic studies also show that women are at least 50% more susceptible to RLS than men and RLS is more common in older adults, although it can occur in some as early as the pre-school years.

This document, when printed, is valid only until its new revision gets released, or when it becomes obsolete in the eQMS. The user of a printed copy of this document is responsible for using the current revision and for discarding superseded or obsolete revisions. The most current version of this document always resides in the eQMS.

Noctrix Health, Inc. CONFIDENTIAL CL-7 v2.0

The current standard of care involves initial prescription of dopaminergic medications – such as Requip, Mirapex, and Neupro – that initially provide symptomatic relief but often become ineffective over continued usage⁴. Tolerance to these medications is rapid and well-documented⁵; approximately 10% of patients per year become refractory to these medications, and fewer than 20% patients have sustained benefits lasting 10 years or longer⁶. It is also now understood that dopaminergic medications cause what is known as "augmentation", or paradoxical progressive worsening of RLS symptoms that is much faster than the natural progression of the condition. Due to augmentation, patients on dopaminergic medications require increasingly higher doses⁷. Maximal dosage is limited by an increasing risk of side-effects at higher doses, which include compulsive behaviors including substance abuse, hypersexuality, and gambling⁸. As a result of these downsides of dopaminergic agents, a minority of clinicians are starting to prescribe gabapentinioids (e.g., Horizant) as an alternative first-line of treatment; these medications do not typically lead to augmentation but confer risks such as respiratory depression⁹, dizziness, and somnolence during the day.

For the large subpopulation of patients who become refractory to dopaminergic medications – typically due to augmentation – there are no FDA approved treatment options and no safe treatment options. As a result of tolerance, augmentation, and dosage limitations, RLS patients often continue to suffer from moderate-severe RLS symptoms while continuing to be reliant on high doses of dopaminergic medications to provide a small degree of relief. To address the massive unmet need, the leading clinicians involved with RLS advocate prescribing off-label opioids¹⁰. The leading options, oxycodone and methadone, have well documented risks, which include addiction, dependence, overdose, and occasionally death. This situation is especially concerning because primary RLS typically starts in middle age or earlier and persists throughout life, thus patients may end up reliant on opioids for the final decades of their lives.

The investigational device – the NTX100 Neuromodulation System – is a high-frequency tonic motor activation (hf-ToMAc) system developed by Noctrix Health, Inc. (Sponsor). The system is positioned bilaterally on the lower legs over the head of the fibula bone, a position where the peroneal nerve is closest to the skin.

This study evaluates the effects of NTX100 on the symptoms of RLS during in-home subject-administered stimulation. This approach is useful for evaluating safety, usability, tolerability, and efficacy in a realistic environment.

2.0 STUDY OBJECTIVE

The study objective is to assess longer-duration efficacy, tolerability, and adherence for patients with moderate to severe medication-refractory RLS with the NTX100 Neuromodulation System (NTX100).

3.0 STUDY DESIGN

[figure not shown]
3.1 Overview

Subjects who previously completed the RESTFUL Study [Protocol Number: CT-04; ClinicalTrials.gov Identifier: NCT04874155] consent to one of two Arms, the design of which is

illustrated in the flowchart below (Figure 1). Arm 1 is a Direct Roll-Over Extension and Arm 2 is a Control.

- **Arm 1** (Direct Roll-Over Extension) Arm 1 is only an option for subjects who successfully complete RESTFUL Study after enrollment to CT-05 begins at a given clinical site; Arm 1 involves a 24-wk extension period of NTX100 device use followed by an 8-wk period without device use. Subjects in Arm 1 are instructed to maintain constant dose and schedule of RLS medication (if applicable).
- Arm 2 (Control Group) Arm 2 is an option for subjects who successfully complete the RESTFUL Study before enrollment to CT-05 begins at a given clinical site or subjects who decline to participate in Arm 1. Subjects enrolled in Arm 2 will receive no treatment with the NTX100 device during Arm 2. Arm 2 involves assessment during the 24-wks after RESTFUL Study completion. Subjects in Arm 2 are permitted to change RLS medication.

Figure 1: Study Design Flowchart

The schedule of assessments for this study is presented in Table 1.

Table 1: Schedule of Assessments

	Eval 1			Eval 2	Eval 3	Eval 4	Eval 5	Eval 6	Eval 7	Eval 8	Eval 9	
	Day 0	Wks 1-24	Wks 25-32	Wk-2	Wk-4	Wk-8	Wk-12	Wk-16	Wk-20	Wk-24	Wk-32	
	In-person	Remote	Remote	Remote	Remote	In-person or Remote**			Remote	In-person	Remote	
Completed by												
	X											
	X											
Staff + subject	X											
Subject		X										
Subject			х									
Staff				X	X	x	X	x	X	X		
Staff	X			Х	Х	x	X	Х	Х	х	X	
Staff				X	Х	x	X	x	X	Х	X	
Staff + subject				Х	Х	x	Х	Х	Х	х	X	
Staff + subject				X	X	x	X	x	X	X	X	
Investigator + subject						х		х		Х	X	
Staff + subject					Х	x	X	Х	х	х	X	
Staff + subject	X									х		
Staff + subject										х		
Staff + subject											X	
Staff + subject	X **					X **		X **				
	* Data from Eval	11 of the RE	STFUL Study	will be us	ed, since b	oth Evals typic	cally occu	r on the same	day			
	Staff + subject Subject Subject Staff Staff Staff Staff Staff + subject Staff + subject Investigator + subject Staff + subject	In-person	Day 0 Wks 1-24 In-person	Day 0	Day 0 Wks 1-24 Wks 25-32 Wk-2	Day 0	Day 0	Day 0	Day 0	Day 0 Wks 1-24 Wks 25-32 Wk-2 Wk-4 Wk-8 Wk-12 Wk-16 Wk-20 In-person or In-pe	Day 0 Wks 1-24 Wks 25-32 Wk-2 Wk-4 Wks-4 Wks-12 Wk-16 Wk-20 Wk-24	Day 0

		Eval 1	Eval 2	Eval 3	Eval 4	
		Day 0	Wk-8*	Wk-16*	Wk-24*	
		In-person or				
Assessment	Completed by	Remote	Remote	Remote	Remote	
Screening		X				
Consent		X				
Study entry questionnaire	Staff + subject	X				
ConMeds	Staff	X	Х	X	X	
AE Monitoring/Reporting	Staff		Х	Х	X	
IRLS	Staff + subject		Х	Х	X	
PGI-I	Staff + subject		Х	Х	X	
CGI-I	Investigator		Х	Х	X	
MOS-Sleep	Staff + subject		Х	Х	X	
SF-36	Staff + subject	X			X	
Study exit questionnaire	Staff + subject				Х	

^{*} If EVAL 1 spans multiple days, Day 0 refers to the final day of EVAL 1.

3.2 Method of Assigning Subjects to Treatment

All subjects who are enrolled in Arm 1 will be assigned to:

- NTX100 programmed to ACTIVE mode for Weeks 1-24
- No treatment for Weeks 25-32

and will be instructed to maintain constant dosage and schedule of RLS medication (if applicable) for Week 1-32.

All subjects who are enrolled in Arm 2 will be assigned to:

• No treatment for Weeks 1-24 and will be permitted to change RLS medication during the study.

3.3 Blinding

The study is open-label and there will be no blinding. All subjects and staff will be informed that NTX100 is programmed to ACTIVE mode.

3.4 Determination of Sample Size

No sample size determinations were made. Enrollment was based on consent rate from subjects who completed the RESTFUL study after this study was open to enrollment.

3.5 Changes to the Protocol-Specified Analyses

SAP Version 1.0.

No changes were made to the analysis of the primary efficacy endpoint or key secondary efficacy endpoints #1-5 specified in the protocol. The definition, ordering, and statistical treatment of each remains the same. Consistent with the protocol, the intent-to-treat population will be used to analyze the primary and key secondary efficacy endpoints.

The following changes and additions were made to key secondary analyses:

- 1. Key secondary endpoints #6-11 were added, comparing Arm 1 to Arm 2 at Week 24.
- 2. The Stable Medication (SM) Population was added as a mechanism for additional supportive analysis. This is intended to account for the differences in instructions regarding changes to prescription medications affecting RLS and/or sleep for Arms 1 and 2.
- 3. The definition of the Per Protocol Population was simplified.

Additional clarifications, additions, and modifications were made that do not affect the statistical treatment of the primary or key secondary endpoints.

SAP Version 2.0.

1. For the primary efficacy endpoint (CGI-I Responder Rate), the original null hypothesis was that the Responder Rate is equal to 0 and the null hypothesis was that the Responder Rate is greater than 0. Since a single observation of a Responder would disprove this null hypothesis, this hypothesis test is not a meaningful analysis. Therefore, for the primary

- efficacy endpoint, hypothesis testing has been replaced with presentation of 95% confidence intervals.
- 2. The same issue affected the first key secondary efficacy endpoint (PGI-I Responder Rate) and thus the same change was made.
- 3. As a result of changes 1-2, hierarchical hypothesis testing began with the second key efficacy endpoint (IRLS total score).
- 4. Tables were expanded to include 95% confidence intervals for each key secondary endpoint.

Additional clarifications, additions, and modifications were made that do not affect the statistical treatment of the primary or key secondary endpoints.

4.0 EFFICACY ENDPOINTS

4.1 Primary Efficacy Endpoint

The primary efficacy endpoint is the response on the Clinical Global Impressions-Improvement (CGI-I) scale at Week 24 of Arm 1 relative to entry to the RESTFUL Study. A "successful" response for the 7-point CGI-I scale will be defined as a response of "Much Improved" or "Very Much Improved".

4.2 Key Secondary Efficacy Endpoints

The key secondary efficacy endpoints are as follows:

Comparisons between Arm 1 Week 24 and Baseline (entry to the RESTFUL Study):

- 1. PGI-I responder rate (defined as for CGI-I) at Week 24 of Arm 1 relative to entry to the RESTFUL Study.
- 2. Mean reduction in IRLS total score at Week 24 of Arm 1 relative to entry to the RESTFUL Study.
- 3. Mean reduction in MOS-II score at Week 24 of Arm 1 relative to entry to the RESTFUL Study.
- 4. Mean reduction in MOS-I score at Week 24 of Arm 1 relative to entry to the RESTFUL Study.
- 5. Frequency of RLS symptoms (based on IRLS question #7) at Week 24 of Arm 1 relative to entry to the RESTFUL Study.

Comparisons between Arm 1 Week 24 and Arm 2 Week 24:

- 6. CGI-I responder rate (defined as for CGI-I) at Week 24 of Arm 1 compared to Week 24 of Arm 2.
- 7. PGI-I responder rate (defined as for CGI-I) at Week 24 of Arm 1 compared to Week 24 of Arm 2.
- 8. Mean reduction in IRLS total score at Week 24 of Arm 1 compared to Week 24 of Arm 2.
- 9. Mean reduction in MOS-II score at Week 24 of Arm 1 compared to Week 24 of Arm 2.
- 10. Mean reduction in MOS-I score at Week 24 of Arm 1 compared to Week 24 of Arm 2.
- 11. Frequency of RLS symptoms (based on IRLS question #7) at Week 24 of Arm 1 compared to Week 24 of Arm 2.

5.0 STATISTICAL CONSIDERATIONS

5.1 General Methodology

The statistical analysis of the data obtained from this study will be performed using R statistical software version 4.2.1 or higher. Descriptive statistics may be calculated using Microsoft Excel instead of R.

Data collected in this study will be documented using summary tables and subject data listings. For all efficacy analysis, continuous variables will be summarized using descriptive statistics, specifically the mean, median, standard deviation, minimum and maximum. Categorical variables will be summarized using frequencies and percentages. For continuous data, the minimum and the maximum will use the same decimal place accuracy as the raw data. The mean, median, and standard deviation will be reported to a minimum of one more decimal place than the raw data; statistics for sub-scores may be reported to two more decimal places than the raw data. For categorical data, percentages will be reported to one decimal place. P-values will be reported to 4 decimal places. P-values less than 0.0001 will be displayed as <0.0001 in the tables. All statistical tests for efficacy will be performed at the one-sided 0.025 significance level, and all statistical tests for safety (adverse events) will be performed at the two-sided 0.05 significance level.

For all tables comparing efficacy outcome measures between Arm 1 and Arm 2, effect sizes will be summarized based on Cohen's d for means and Cohen's h for proportions. Additionally, for all tables comparing efficacy outcome measures between Arm 1 Week 24 and CT-05 study entry, effect sizes will be summarized based on Cohen's d for means and Cohen's h for proportions.

Data listings will be sorted by Arm, site number, and subject ID number.

5.2 Adjustments for Covariates

There will be no adjustment for covariates in any efficacy or safety analysis.

5.3 Handling of Dropouts and Missing Data

If there are any missing data for efficacy endpoints, the "Last Observation Carried Forward" imputation method will be used to impute the missing data. If no data are available in this study, then the last observation from CT-04 will be carried forward.

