16.1. Overview

Arms 1 and 3 involve a 24-week extension of in-home investigational device usage for subjects who previously completed the RESTFUL Study, followed by an 8-week period without investigational device usage to assess the progression of RLS following cessation of treatment. Two separate arms are employed to maximize the number of subjects eligible for any extension phase (Arm 1 and Arm 3) while also maximizing the number of subjects who can proceed directly to the extension phase (Arm 1 only). Notably, in the RESTFUL Study, subjects will have already completed either 4-weeks of device usage (Sham \rightarrow Active) or 8-weeks (Active \rightarrow Active) depending on randomization. Since site staff were blinded to RESTFUL Study treatment assignment, no procedures in this protocol will be affected by RESTFUL Study treatment assignment.

Arm 2 serves as a control arm with matched duration to the 24-week period of investigational device usage; this arm is designed to the assess the changes to medication and RLS symptoms that occur under the conventional standard of care, in the absence of investigational device intervention. Although the duration of Arm 2 states 24-weeks, each subjects participation will vary, since the 24-week period also includes the time between when the subject exits the RESTFUL study and when they enroll in Arm 2 of the CT-05 study. For example, subjects who are consented more than 8-wks after RESTFUL Study completion will only complete the remaining follow-ups (e.g. subjects consented 12-wks after the RESTFUL Study will only complete the 16-wk and 24-wk follow-ups).

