16.12. Evaluation and study assessment schedule

Investigational Plan, Protocol CT-05 (Extension Study)

Document #: CT-4

Rev: 1.0

Effective: 11/24/2021

The following evaluation calls and/or visits are scheduled, as outlined in Tables 4 and 6 below. A window of +/- 4 days may be utilized on office follow-ups and a window of +/- 2 days for any phone follow-up, as needed. To reduce self-selection bias, is important to incentivize maximal participation of subjects from the RESTFUL Study in this study. One method to incentivize participation is to reduce the requirement for in-person visits, which can be especially challenging for subjects who do not live within a short distance of the clinical site.

Arms 1 and 3:

Evaluation 1: In-person visit for enrollment, including consent, screening, and assessments. For Arm 1, consent & screening will typically occur on the same visit as Eval 11 for the RESTFUL Study. If the subject's schedule does not permit completion of assessments during this office visit, then these assessments may be conducted via phone follow-up at any time within the 3-days following the office visit.

Evaluation 2: (2-wks after Eval. #1) Phone follow-up to assess RLS symptoms, NTX100 use and assess the occurrence of adverse events and/or changes to daily medications.

Evaluation 3: (4-wks after Eval #1) Phone follow-up to assess RLS symptoms, NTX100 use, and assess the occurrence of adverse events and/or changes to daily medications.

Evaluation 4: (8-wks after Eval #1) In-person visit or Phone call* follow-up to assess RLS symptoms, NTX100 use, and assess the occurrence of adverse events and/or changes to daily medications. Device replacement* and device log analysis may occur at this Evaluation, but this is not a strict requirement.

Evaluation 5: (12-wks after Eval #1) Phone follow-up to assess RLS symptoms, NTX100 use, and assess the occurrence of adverse events and/or changes to daily medications.

Evaluation 6: (16-wks after Eval #1) In-person visit or Phone call* follow-up to assess RLS symptoms, NTX100 use, and assess the occurrence of adverse events and/or changes to daily medications. Device replacement* and device log analysis may occur at this Evaluation, but this is not a strict requirement.

Investigational Plan, Protocol CT-05 (Extension Study)

Document #: CT-4

Rev: 1.0

Effective: 11/24/2021

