Evaluation 7: (20-wks after Eval #1) Phone follow-up to assess RLS symptoms, NTX100 use, and assess the occurrence of adverse events and/or changes to daily medications.

Evaluation 8: (24-wks after Eval #1) In-person follow-up to assess RLS symptoms, NTX100 use, and assess the occurrence of adverse events and/or changes to daily medications. Devices are returned at this time.

Evaluation 9: (32-wks after Eval #1) Phone follow-up to assess RLS symptoms, adverse events, and any changes to daily medications. Study exit occurs at this time.

* See Section 16.13 below for discussion of device replacement and in-person visits.

In addition to these assessments, subjects will complete a Weekly Questionnaire each week throughout the 24-wk duration of device usage and a Bi-weekly Questionnaire every 2-weeks from Weeks 25-32.

The schedule of assessments are shown in Table 4 below. Additionally, the devices may automatically log quantitative compliance, usage data, and leg movement data throughout the duration of the study.

Table 4. Schedule of Assessments for Arms 1 and 3

Investigational Plan, Protocol CT-05 (Extension Study)

Document #: CT-4

Rev: 1.0

Effective: 11/24/2021

		Eval 1 Day 0	Wks 1-24	Wks 25-32	Eval 2 Wk-2	Eval 3 Wk-4	Eval 4 Wk-8 In-person or	Eval 5 Wk-12	Eval 6 Wk-16 In-person or	Eval 7 Wk-20	Eval 8 Wk-24	Eval 9 Wk-32
		In-person	Remote	Remote	Remote	Remote	Remote**	Remote	Remote**	Remote	In-person	Remote
Assessment	Completed by											
Screening		X										
Consent		X										
Study entry												
questionnaire	Staff + subject	X										
Weekly questionnaire	Subject		X									
Biweekly questionnaire	Subject			X								
Review weekly												
questionnaire												
responses	Staff				X	Х	X	Х	X	Х	X	
ConMeds	Staff	X			X	X	X	Х	X	Х	X	X
AE Monitoring/Reporting	Staff				Х	Х	X	X	X	X	X	X
RLS	Staff + subject	X (Arm 3 only*)			X	X	X	X	X	Х	X	X
PGI-I	Staff + subject				X	Х	X	X	X	Х	X	X
CGI-I	Investigator + subje	ect					X		X		Х	X
MOS-Sleep	Staff + subject	X (Arm 3 only*)				X	X	Х	Х	Х	Х	X
SF-36	Staff + subject	X									Х	
Device completion												
questionnaire	Staff + subject										X	
Study exit questionnaire	Staff + subject											X
Device replacement Sta	Staff + subject	X **					X **		X **			
		* For Arm 1, data	from Eval	11 of the RE	STFUL Stu	dv will be	used, since bo	th Evals	typically occ	ur on the	same day	

Arm 2:

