16.16. Subject Discontinuation

A subject may be removed from the study prior to completion for any of the following reasons:

- Voluntary withdrawal of consent
- Adverse event preventing further study participation
- Investigator believes risk of further subject participation outweighs benefit
- Persistent non-compliance or lost to follow-up
- Pregnancy
- Subject no longer meets inclusion criteria
- [For arms 1 and 3 only] Subject makes a significant change to dosage of medications known to interfere with sleep or RLS symptoms, including sleep medications, antidepressants, sedative antihistamines.

Investigational Plan, Protocol CT-05 (Extension Study)

Document #: CT-4

Rev: 1.0

Effective: 11/24/2021

• [For arms 1 and 3 only] Insufficient device availability (see 16.16.1 below)

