16.16.1. Discontinuation related to device availability

As noted in Section 11, the investigational device may include components that are consumable or semi-consumable and may be replaced on a periodic or as-needed basis. In the unlikely event that investigational device supply becomes insufficient to replenish the consumable components of the devices for all subjects enrolled in the study, enrollment will be paused and device replacement will continue in a normal manner until the device supply for the study is exhausted (or nearly exhausted). At that point, remaining subjects will be removed from the study at their next scheduled device replacement timepoint.

Additionally, it is possible that some patterns of device use or misuse may lead to a reduction in the functional lifespan of the investigational device below 8-weeks. If this is suspected for a specific subject, that subject may be removed from the study.

The Investigator or research staff will complete a study exit form in the eCRF for any subject who prematurely discontinues from the study. If discontinuation was the result of an AE, the AE will also be recorded in the eCRF.

Upon discontinuation, subjects will receive partial compensation commensurate with their completed Phases.

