6.0 ANALYSIS POPULATIONS

6.1 Intent-to-Treat (ITT) Population

The Intent-to-Treat (ITT) Population will include all eligible subjects who pass screening and are enrolled into the study. The ITT Population Set will be used for the primary analysis of all efficacy endpoints.

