8.0 EFFICACY AND SAFETY ANALYSES

8.1 Primary Efficacy Endpoint Analysis

The primary efficacy endpoint is the response on the Clinical Global Impressions-Improvement (CGI-I) scale at Week 24 of Arm 1 relative to Baseline (RESTFUL study entry) where a "successful" response is defined as a response of "Much Improved" or "Very Much Improved". This endpoint will be summarized by treatment group using frequencies and percentages.

The 95% confidence interval will be presented for the proportion of "successful" responses. If there are any missing data for this endpoint, last observation carried forward (LOCF) methods will be used to impute the missing data.

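### Missing Week 24 values are filled by LOCF with a RESTFUL fallback, and no planned analysis allows for lost response in the subjects concerned

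*SAP*

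**What the plan says.** SAP 5.3 applies LOCF to every efficacy endpoint and then adds: "If no data are available in this study, then the last observation from CT-04 will be carried forward". SAP 8.1 repeats the rule for the primary CGI-I endpoint: "last observation carried forward (LOCF) methods will be used to impute the missing data". SAP 6.1 settles where it acts: "The ITT Population Set will be used for the primary analysis of all efficacy endpoints".

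On the fallback value, Protocol 16.1 says that in RESTFUL "subjects will have already completed either 4-weeks of device usage" (sham, then active) or 8 weeks (active in both periods). Either way the last period is on active device.

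Two supportive populations are defined. The Per Protocol set is used for all efficacy endpoints and excludes subjects who discontinue or lack endpoint data. The Stable Medication set is used for key secondary endpoints #6-11 and selects on reported medication changes. The SAP text and its list of tables name no other analysis of missing data. Protocol 17.2.3 mentions multiple imputation only as an option. SAP 3.4 reports no sample size calculation, and neither document states an expected responder rate or missing fraction.

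**The concern.** The objective is longer-duration efficacy. For a subject not seen at Week 24, LOCF supplies an earlier rating, so for that subject durability is assumed and not observed. SAP version 2.0 replaced the primary test with a 95% confidence interval, so the filled values go straight into the headline proportion. They also count as observed, so the interval does not reflect the missing information.

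Loss related to response is possible. Under Protocol 16.16, in Arms 1 and 3 only, a significant dosage change in medication that affects sleep or RLS symptoms is a ground for removal. Such a change can follow worsening, and LOCF would then keep the earlier on-device score.

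Arm 2 exists to show the course without the device. A RESTFUL value carried to its Week 24 is an outcome on the wrong treatment.

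**Working it through.** **No plan figure to reproduce.** All rates and fractions below are assumptions.

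**1. What is carried in Arm 1** (Protocol 16.12, Table 4; fallback read per endpoint)

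| Endpoint | First CT-05 rating after entry | When the CT-04 value is used |
|---|---|---|
| CGI-I (primary) | Week 8 | no CGI-I from Week 8 on |
| PGI-I, IRLS, IRLS item 7 | Week 2 | nothing from Week 2 on |
| MOS-I, MOS-II | Week 4 | nothing from Week 4 on |

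The primary endpoint is the most exposed: a subject lost before Week 8 enters with a RESTFUL CGI-I. For IRLS and MOS, Protocol 16.2 and the Table 4 footnote take RESTFUL Eval 11 as the entry value, typically from the same day. The fallback there is in effect the CT-05 entry score.

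**2. Reach in Arm 2** (Protocol 16.2, and 16.12 with Table 5). Subjects enrolling 8, 16 or 24 weeks after RESTFUL have an off-device evaluation due at that point. The fallback therefore mainly reaches 0-week enrollees who miss every later call.

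**3. Shift in the Arm 1 responder rate** = m × (carried rate - true rate), where m is the fraction missing Week 24.

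| Assumption | m = 10% | m = 20% |
|---|---|---|
| (a) carried 60-70%, true 20-40% | +2 to +5 points | +4 to +10 |
| (b) as (a), but half of the loss unrelated to response | +1 to +2.5 | +2 to +5 |
| (c) all loss unrelated to response | 0 | 0 |
| (d) carried values already poor, 20-30%; true 20-40% | -2 to +1 | -4 to +2 |

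For (a) at 10%: 0.10 × (0.60 - 0.40) = 0.02 and 0.10 × (0.70 - 0.20) = 0.05. For (d) at 10%: 0.10 × (0.20 - 0.40) = -0.02 and 0.10 × (0.30 - 0.20) = +0.01.

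**4. Interval width.** At the same rate, the LOCF interval is narrower than one from observed values by 1 - √(1 - m): 5.1% at 10% missing and 10.6% at 20%.

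**5. Does Per Protocol bound the effect?** Assume N = 40 and 75% response in completers.
- 20% missing: 24 of 32 completers respond and 6 of 8 carried values are responses. LOCF = 30/40 = 75.0% (Wilson 95% CI 59.8 to 85.8). Per Protocol = 24/32 = 75.0%. Missing scored as non-response = 24/40 = 60.0% (44.6 to 73.7).
- 30% missing: 21 of 28 completers respond and 6 of 12 carried values are responses. LOCF = 27/40 = 67.5%, Per Protocol = 21/28 = 75.0%, non-response = 21/40 = 52.5%.

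Per Protocol can equal or exceed LOCF, so agreement between the two says little about lost response.

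**6. Arm 1 versus Arm 2.** If a fraction f of Arm 2 takes the fallback, with the rates in (a), the control rate rises by f × (0.20 to 0.50): 0.4 to 1.0 points at f = 2%, and 1.0 to 2.5 at f = 5%. That narrows the difference. Ordinary LOCF in both arms can act either way. As a direction check only, assume 40 per arm, completer rates of 70% and 40%, and carried values at 70% in both arms:
- Missing 20% in Arm 1 and 0% in Arm 2: LOCF difference 30 points (one-sided p = 0.0035); non-response scoring 16 points (p = 0.076).
- Missing 10% in Arm 1 and 20% in Arm 2: LOCF 24 points (p = 0.015); non-response scoring 31 points (p = 0.003).

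**The case against.** Much of the case on the other side stands.

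- A reader might infer that every planned analysis rests on carried values. That is not so: Per Protocol is a planned analysis without them, and its contrast with ITT shows what the filled subjects contribute. What survives is narrower: it removes those subjects and never considers that they lost response.
- A reader might infer that the primary value is undefined for a subject with, say, a Week 2 PGI-I but no CGI-I. That needs the fallback to mean no CT-05 data of any kind. SAP 5.3 opens with missing endpoint data, so the per-endpoint reading is the natural one.
- The evidence for response-related loss is limited. The removal rule in Protocol 16.16 is permissive, and its named examples are sleep medications, antidepressants and sedative antihistamines. The Per Protocol definition lists medication change separately from discontinuation, so such subjects may stay and be observed at Week 24. Other loss need not bias at all: if device supply runs out, "remaining subjects will be removed from the study at their next scheduled device replacement timepoint".
- Missingness may be low. Exclusion criterion 25 screens out subjects who missed two or more RESTFUL follow-ups, and most visits can be remote.
- LOCF breaks no protocol commitment, since multiple imputation was only optional. The primary endpoint and #1 carry no test, so no pass or fail turns on them.

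These points limit the size of the problem. They do not supply the missing sensitivity analysis or justify an on-device value as an Arm 2 outcome.

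**Conclusion.** The concern holds in a limited form. The text is clear that the primary ITT analysis assumes persistence for Arm 1 subjects missing Week 24, that the fallback can place an on-device value in the no-device arm, and that no planned analysis assigns lost response to the subjects concerned.

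The size is unknown. Under the assumed rates, the Arm 1 shift at 10% missing is about -2 to +5 points, with zero possible. A reader might infer that the plan inflates the headline rate or favours the device. The documents do not support that. The sign depends on why subjects are lost and on how good their carried values were. The Arm 2 fallback tends to work against the device if on-device values are better, and the net direction for #6-11 is open. Nor is the gap between LOCF and non-response scoring (6 to 7 points at 10% missing with carried rates of 60-70%) a measure of bias, since non-response scoring is itself a bound. The point should be fixed because the effect cannot be judged from what is planned.

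**What to change.** 1. Do not use a CT-04 value as the Week 24 outcome in Arm 2. Do not carry it as the outcome in Arm 1 either, but keep end-of-RESTFUL status as a predictor if a model-based imputation is used. State how a subject with no CT-05 value for an endpoint then enters the ITT analysis.
2. Prespecify at least one sensitivity analysis that does not assume persistence: missing Week 24 scored as non-response for CGI-I and PGI-I, and a delta or tipping-point shift for IRLS and MOS. Treat the same Arm 1 rate alike wherever it appears (primary and #6; #1 and #7).
3. Report the number of LOCF-filled Week 24 values by endpoint and arm, with any CT-04 values shown separately.

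LOCF may remain the main or a supportive analysis. Replacing it with multiple imputation is optional and no cure by itself: if dropouts are drawn at 60-70% when their true rate is 20-40%, the error is the same +2 to +5 points at 10% missing.

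The cost is a SAP edit, modest programming and a sensitivity estimate that may look less favourable. Non-response scoring must be labelled a bound. At 10% missing with the rates in (a), it errs by -2 to -4 points if all loss is informative. If half is unrelated to response, it errs by -(0.05 × 0.60 + 0.05 × 0.20) = -4 to -(0.05 × 0.70 + 0.05 × 0.40) = -5.5 points, which is further from the truth than LOCF's +1 to +2.5.
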